	 activities OR hospitalized pending disposition, not requiring COVID-related care; 3, hospitalized, not requiring supplemental oxygen; 4, hospitalized, requiring supplemental oxygen; 5, hospitalized, requiring nasal high-flow oxygen therapy, noninvasive mechanical ventilation, or both; 6, hospitalized, requiring ECMO, invasive mechanical ventilation, or both; and, 7, death. Change in biomarker levels (CCL5, IL-6, Chi311, etc) from time of enrollment to completion of therapy or live discharge from the hospital (whichever comes first) 7-, 14- and 28-day all-cause-mortality 	
	Days on mechanical ventilation	
SAFETY EVALUATIONS	Daily, multi-disciplinary safety monitoring with interim analysis after 8 subjects have received four or more doses of Maraviroc.	
PLANNED INTERIM ANALYSES	Exposure-adjusted rates of adverse events and those resulting in discontinuation will be calculated at the point in which 8 patients have received more than four doses of treatment. Serious adverse events will be monitored by the study team on an ongoing basis throughout the study.	
STATISTICS Analysis Plan	 Rates of adverse events by severity and rate of completion of therapy. Change in biomarkers compared to clinical improvement Percent of study population reaching clinical improvement at Day 7 will be compared to published results from Remdesivir for 5 or 10 Days in Patients with Severe COVID-19, and other available clinical trials including The Randomized Evaluation of COVID-19 therapy (RECOVERY) Trial. 	

Version #: 2.8 Version Date: 11/6/2020 Page 4 of 30

TABLE OF CONTENTS

1	BACKGROUND7		7
2	STUDY RATIONALE9		
3 STUDY OBJECTIVES			10
	3.1	Primary Objective	10
	3.2	Secondary Objectives	10
4	STUI	DY DESIGN	10
	4.1	Study Overview	10
5	CRIT	TERIA FOR EVALUATION	10
	5.1	Primary Efficacy Endpoint	10
	5.2	Secondary Efficacy Endpoints	10
6	SUB	JECT SELECTION	11
	6.1	Study Population	11
	6.2	Inclusion Criteria.	11
	6.3	Exclusion Criteria	11
7	CON	CURRENT MEDICATIONS	11
	7.1	Allowed	11
	7.2	Prohibited	12
8	STUI	DY TREATMENTS	12
	8.1	Method of Assigning Subjects to Treatment Groups	12
	8.2	Formulation of Test Product	12
	8.3	Supply of Study Medication at the Site	12
	8.4	Study Medication Accountability	13
	8.5	Measures of Treatment Compliance	14
9	STUI	DY PROCEDURES AND GUIDELINES	14
	9.1	Clinical Assessments	14
	9.2	Clinical Laboratory Measurements	15
	9.3	Research Laboratory Measurements	15
10	EVA	LUATIONS BY VISIT	16
	10.1	Screening/Enrollement (Day 0).	16
	10.2	Visit 1 (Day 1)	16

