3.2 Secondary Objectives

The secondary objective is to investigate the relationship between reduction of inflammatory markers (such as IL-6, CCL5, etc.) and clinical outcomes, including avoidance of respiratory decompensation and death.

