5.2 Secondary Endpoints

- Time to clinical improvement, defined as time from enrollment to an improvement of two points on a seven-category ordinal scale (defined below) or live discharge from the hospital, whichever comes first
 - Ordinal scale: 1, not hospitalized with resumption of normal activities; 2, not hospitalized, but unable to resume normal activities OR hospitalized pending disposition, not requiring COVID-related care; 3, hospitalized, not requiring supplemental oxygen; 4, hospitalized, requiring supplemental oxygen; 5, hospitalized, requiring nasal high-flow oxygen therapy, noninvasive ventilation, or both; 6, hospitalized, requiring ECMO, invasive mechanical ventilation, or both; and, 7, death.
- Change in cytokine levels from time of enrollment to completion of therapy or live discharge from the hospital (whichever comes first)
- 7-, 14- and 28-day all-cause-mortality
- Time to improvement to Score of 2 or less (days)
- Days on mechanical ventilation

Version #: 2.8 Version Date: 11/6/2020 Page 10 of 30

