10.4 Visit 3 (Day 3)

- Review and document Medication Administration Record for Day 2 of study.
- Perform interview with patient. Record any Adverse Events.
- Document complete physical exam.
- Perform and record vital signs.
- Perform and record oximetry on room air and on current oxygen-delivering device.
- Record any events including transfer to intensive care, intubation, hospice referral.
- Document laboratory values and imaging obtained as part of routine standard of care.
- Collect blood sample for research laboratory test(s): Biomarkers.

Version #: 2.8 Version Date: 11/6/2020 Page 16 of 30

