10.11 Day of Discharge

- Perform interview with patient. Record any Adverse Events.
- Perform and record vital signs.
- Perform and record oximetry on room air and on current oxygen-delivering device.
- Document laboratory values and imaging obtained as part of routine standard of care.
- Record discharge destination, oxygen requirement at time of discharge.
- Obtain research labwork if discharge occurs earlier than Day 15

Version #: 2.8 Version Date: 11/6/2020 Page 18 of 30

• Schedule post-discharge phone follow-up.

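### The cytokine-change interval ends early for subjects discharged before completing therapy, so comparing the pooled change with clinical improvement mixes marker trajectory with interval length, in a direction the documents cannot settle.

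*Combined protocol and SAP*

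**What the plan says.** **The endpoint.** Section 5.2 lists "Change in cytokine levels from time of enrollment to completion of therapy or live discharge from the hospital (whichever comes first" as a secondary endpoint. The synopsis applies the same rule to named biomarkers. A full course is seven days (Section 4.1), so for a subject who stays and takes all of it the interval nominally ends on Day 7.

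**The outcome.** In the same section, time to clinical improvement ends at a two-point gain on the ordinal scale "or live discharge from the hospital, whichever comes first". Score 1 is out of hospital, and score 2 reads "2, not hospitalized, but unable to resume normal activities OR hospitalized pending disposition". Discharge from score 4 or worse is therefore itself a gain of at least two points.

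**The comparison.** The secondary objective in Section 3.2 is to "investigate the relationship between reduction of inflammatory markers (such as IL-6, CCL5, etc.) and clinical outcomes". The statistics entry of the synopsis lists "Change in biomarkers compared to clinical improvement" and gives no method, time point or pooling rule. The one biomarker model in Section 15.3 regresses ICU and ventilation length of stay on laboratory and biomarker data. It does not mention interval length.

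**The samples.** Section 4.1 plans blood on Day 0, Day 3, Day 7, and Day 15 or live discharge if earlier. Section 10.4 has the Day 3 draw ("Collect blood sample for research laboratory test(s): Biomarkers") and Section 10.11 the discharge draw ("Obtain research labwork if discharge occurs earlier than Day 15"). After discharge, contact is by phone with no blood listed (Section 10.12), and study drug is not continued (Section 12.1). Subjects discharged early because they improved are not replaced (Section 12.4).

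**The concern.** One event, live discharge, does two jobs: it counts as improvement and it closes the window over which the marker is measured. This has two consequences.

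- **Unequal intervals.** A subject discharged on Day 4 has four days in which the marker can change; one who stays has seven. A pooled comparison of the two reflects observation time as well as biology.
- **Timing.** The discharge sample coincides with the outcome, so a fall seen there cannot be said to come before recovery.

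The missing later samples cannot be recovered after discharge. The analysis serves the only secondary objective, and a distorted or wrong-signed association could misdirect follow-on work.

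**Working it through.** The plan states no figure to reproduce. It gives no cytokine trajectory, no variance and no distribution of discharge days. From the documents come the interval rule, the 7-day course, the sampling days and N = 16. Everything else below is assumed.

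**1. Whose interval is shortened**

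| Course | End sample | Interval |
|---|---|---|
| Discharged alive before end of therapy | Discharge | Under 7 days, ends on the outcome |
| Improves two points, stays to end of therapy | Day 7 | Full; sample may follow the improvement |
| Does not improve, stays | Day 7 | Full |
| Dies or stops drug early | Not settled by the rule | Unclear |

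**2. Share of the Day 7 change seen at discharge on day t**

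With log-linear decline the share is t/7. If those discharged decline r times as fast per day, the sign reverses when r < 7/t.

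| t | Share, t/7 | Reversal if r is below |
|---|---|---|
| 3 | 43% | 2.33 |
| 4 | 57% | 1.75 |
| 5 | 71% | 1.40 |
| 6 | 86% | 1.17 |

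As a percentage fall, 1 − 2^(−t/h) for half-life h, Day 4 against Day 7 gives 60% v 80% (h = 3 days), 43% v 62% (h = 5) and 33% v 50% (h = 7), with no true difference between subjects.

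If the decline plateaus, the share is (1 − 2^(−t/h))/(1 − 2^(−7/h)). Here h is the half-life of the approach to the plateau. For h = 2 days it is 71% at Day 3 and 90% at Day 5; for h = 1 day, 88% and 98%.

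**3. Effect on a 16-subject comparison**

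Assumed: 8 subjects discharged on Day 3, 4 or 5 (mean 4), 8 measured at Day 7, decline of 0.10 log units per day in those who stay, between-subject slope SD 0.05, assay SD 0.3, and 20,000 simulated trials. The difference is discharged minus stayers; negative means the discharged fell more.

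| Assumed trajectory | As written | Over a common 7 days |
|---|---|---|
| Equal decline | −0.40 + 0.70 = +0.30 | 0 |
| Discharged decline 1.5 times faster | −0.60 + 0.70 = +0.10 | −0.35 |
| Discharged decline 2 times faster | −0.80 + 0.70 = −0.10 | −0.70 |
| Discharged fall 0.10/day, stayers flat | −0.40 − 0 = −0.40 | −0.70 |
| Discharged fall 0.10/day, stayers rise 0.05/day | −0.40 − 0.35 = −0.75 | −1.05 |
| All rise 0.10/day | 0.40 − 0.70 = −0.30 | 0 |

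With equal decline, the discharged group showed the smaller fall in 88% of simulated trials, against 50% for an unbiased measure. At 1.5 times faster, the sign was wrong in 65%.

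Check on the 88%: the variance is 0.05² × 50/3 + 0.10² × 2/3 + 2 × 0.3² = 0.228 for a discharged subject and 0.05² × 49 + 2 × 0.3² = 0.3025 for a stayer. The standard error is √((0.228 + 0.3025)/8) = 0.26, and 0.30/0.26 is about 1.16, which gives 88%. The artefact is thus only a little larger than the noise.

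**4. Dilution by in-hospital improvers**

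If only a share p of improvers leaves early (mean Day 4) and the rest stay to Day 7, the equal-decline artefact is 0.10 × (7 − 4) × p = 0.30p: 0.075 at p = 0.25 and 0.15 at p = 0.5.

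**5. How many subjects might leave early**

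The only related figure is in Section 1: 6% of the lopinavir-ritonavir arm had a two-point improvement at Day 7. That is 0.06 × 16, about one subject. At the other end, assume exponential discharge times with a median of 7 or 5 days, rounded up to whole days. Then 1 − 2^(−6/7) = 45% to 1 − 2^(−6/5) = 56% leave before Day 7, or 7 to 9 of 16.

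**6. Do the planned samples suffice?**

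With equal decline, the fixed Day 0 to Day 3 difference and the per-day difference are both about 0.00. At 1.5 times faster they are −0.15 and −0.05, the correct sign. A plain per-day rate does assume log-linearity. With a plateau at h = 2 days, Day 4 shows 82% of the Day 7 change, so its apparent daily rate is (0.82/4)/(1/7), about 1.4 times too high relative to stayers.

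**The case against.** The strongest reply is that the bias is inferred from an analysis the plan barely specifies. The synopsis line names no method, and the regression in Section 15.3 is not tied to this endpoint. Section 2 speaks of correlating outcomes with cytokine expression, which does not require the marker change to come first. A detailed SAP is due before the final analysis (Section 15). All planned samples will exist, and the primary endpoint is untouched. This limits the stakes, but nothing in the protocol directs the SAP to deal with unequal intervals, and the endpoint as defined produces them.

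A reader might infer that every improver has a shortened interval. The documents do not support that: only discharge before the end of therapy shortens it, and a subject who improves in hospital and stays has the full seven days.

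A reader might also infer that the comparison will come out reversed. Reversal needs markers that fall at similar rates in both groups. The plan's own rationale (Section 1) is a second, later wave of inflammatory mediators. If that wave left non-improvers' markers flat or rising, the result would be attenuation only.

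Finally, early discharge may be uncommon. The 6% figure points that way, though it measures improvement rather than discharge, and Section 7.1 allows remdesivir and dexamethasone here.

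**Conclusion.** The structural point holds on the wording alone. Subjects discharged before completing therapy contribute a shorter interval that ends on an event counted as improvement, and no analysis rule or later sample corrects this. The pooled change should not be the biomarker measure in the comparison with outcome.

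The size and direction of the bias remain open. Under assumed equal log-linear decline, Day 4 discharge shows 57% of the Day 7 change and the sign can reverse. Plateauing markers shrink the effect, flat or rising markers in non-improvers turn it into attenuation, and markers rising in everyone make it favour improvers falsely. It also scales with the share of improvers who leave early, which the documents do not give. The analysis is secondary and exploratory, so this is a correction worth making rather than a threat to the trial's main result.

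**What to change.** In Section 5.2 and the SAP:

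- **Main comparison.** Do not use the pooled change to discharge or end of therapy as the biomarker measure. Analyse log biomarker levels from all planned samples (Day 0, 3, 7, and Day 15 or discharge) by actual sampling day, for example with a repeated-measures model comparing the rate of change by outcome. Check the straight-line assumption against the data.
- **Support.** Add a landmark analysis relating Day 0 to Day 3 change only to outcomes after Day 3. It should not stand alone: the synopsis objective concerns marker reduction later in the infection, and Day 3 is two days after the first dose (Section 10.2).
- **Description.** Report change to end of therapy or discharge by actual sampling day, not as one pooled number.

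The cost is wording and slightly more analysis, with no new samples. Subjects discharged or dead by Day 3 leave the landmark analysis only and should be listed. If median time to discharge were 7 or 5 days (assumed, exponential), discharge alone would remove 1 − 2^(−3/7) = 26% to 1 − 2^(−3/5) = 34%, or 4 to 5 of 16. With 16 subjects, all of these analyses should be labelled exploratory.

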6 SUBJECT SELECTION

6.1 Study Population

Subjects with a diagnosis of SARS-CoV-2 who meet the inclusion criteria will be eligible for participation in this study.

6.2 Inclusion Criteria

- Male or female ≥ 18 years of age at time of screening
- Documentation of a SARS-CoV-2 diagnosis as evidenced by positive SARS-CoV-2 PCR within twelve days at time of screening
- Chest radiography consistent with multi-focal pneumonia or air-space disease
- Written informed consent obtained from subject and ability for subject to comply with the requirements of the study.
- Subject able to safely swallow pills or receive Maraviroc through a nasogastric or orogastric tube.

6.3 Exclusion Criteria

- Subjects who are pregnant, breastfeeding, or unwilling to practice birth control during participation in the study.
- Subjects with the presence of a condition or abnormality that in the opinion of the Investigators would compromise the safety of the subject or the quality of the data. This includes, but is not limited to, recent myocardial infarction in past 6 months, neurological, psychiatric, endocrine, or neoplastic diseases that are judged to interfere with participation in the study.
- Subjects with known diagnosis of human immunodeficiency virus infection (HIV)
- Subjects enrolled in another interventional trial (including one for COVID-19) that excludes participation in other trials, or includes a potent CYP3A inhibitor of inducer (e.g. lopinavir-ritonavir)
- Subjects with ESRD or severe renal failure who are taking potent CYP3A inhibitors or inducers

7 CONCURRENT MEDICATIONS

7.1 Allowed Medications and Treatments

Diligent medication reconciliation will be performed between the primary inpatient team and study team. Reduction in dose or discontinuation of CYP3A inducers/inhibitors, anti-hypertensive medications, and diuretics at time of enrollment will be considered and individualized to each subject at the discretion of the inpatient team. Remdesivir and dexamethasone, if administered outside of a clinical trial, are allowed.

Version #: 2.8 Version Date: 11/6/2020 Page 11 of 30

7.2 Prohibited Medications and Treatments

The following medications are prohibited during the study and administration will be considered a protocol violation.

- Lopinavir-Tenofovir
- Hydroxychloroquine
- Ivermectin

8 STUDY TREATMENTS

8.1 Method of Assigning Subjects to Treatment Groups

Up to a total of 16 individuals who have been diagnosed with SARS-CoV-2 and agree to participation in the study will be placed on Maraviroc 300 mg twice daily for 7 days. Given design as an early, proof-of-concept trial, all patients will be assigned to the treatment group. There will be no placebo control group; however, patients who are withdrawn from the trial drug will be consented at time of enrollment about continuing biomarker surveillance at standard scheduled monitoring times (Day 0, 3, 7 and the earlier occurring timepoint of discharge or Day 15). Subjects who stop Maraviroc prior to completion of Maraviroc will not be replaced.

By definition, Day 0 is day of enrollment extending to administration of first dose of Maraviroc. Day 1 of study is day of first complete BID dosing of Maraviroc.

8.2 Formulation of Test Product

Maraviroc will be supplied in the same formulation of Selzentry, developed by ViiV Healthcare, a global specialist in HIV established in 2009 by Pfizer and GlaxoSmithKline.

8.3 Supply of Study Drug at the Site

Pfizer will reimburse for study drug obtained by Lifespan Pharmacy.

8.3.1 Dosage/Dosage Regimen

- Maraviroc 300 mg twice a day for patients not on concomitant moderate or strong CYP3A inhibitors/inducers.
- Maraviroc 150 mg twice daily for patients unable to tolerate 300 mg twice daily and for patients on moderate or strong CY3PA inhibitors.
- Maraviroc 600 mg twice daily for patients on moderate or strong CY3PA inducers.

8.3.2 Dispensing

Maraviroc will be dispensed by a Pharmacist at the trial site.

Version #: 2.8 Version Date: 11/6/2020 Page 12 of 30

8.3.3 Administration Instructions

Maraviroc can be administered twice a day by mouth with or without food. Maraviroc can also be crushed, mixed with 60 mL sterile water, and administered through a nasogastric or orogastric tube. Documentation of administration will be recorded as per standard protocol of the inpatient unit.

8.4 Measures of Treatment Compliance

Medication Administration records from site's Electronic Medical Record will be audited daily to ensure treatment compliance.

9 STUDY PROCEDURES AND GUIDELINES

Prior to conducting any study-related activities, written informed consent and the Health Insurance Portability and Accountability Act (HIPAA) authorization must be signed and dated by the subject.

9.1 Clinical Assessments

9.1.1 Concomitant Medications

All concomitant medication and concurrent therapies will be documented during the Screening/Enrollment Visit (Day 0), during Study Days 1-8, and at early termination when applicable. Dose, route, unit frequency of administration, and indication for administration and dates of medication will be captured.

9.1.2 Demographics

Demographic information (date of birth, gender, race) will be recorded at enrollment.

9.1.3 Medical History

The follow will be recorded at Screening:

- Date of onset and presence of symptoms related to SARS-CoV-2 infection including cough, shortness of breath, fatigue, nausea, vomiting, diarrhea, rash, abdominal pain, fever, chills, loss of smell, etc.
- History of obesity, hemodialysis, cardiovascular diseases (hypertension, known valvular disease, cardiomyopathies and/or LV systolic or diastolic dysfunction), pulmonary disease (including OSA, COPD, asthma, interstitial lung disease, cystic fibrosis, bronchiectasis, lung transplant, lung cancer, pulmonary hypertension).

9.1.4 Physical Examination

A complete physical examination will be performed by an Investigator who is a physician at time of enrollment. As to reduce healthcare worker exposure to SARS-CoV-2, Investigators may perform an abbreviated physical exam at each visit and utilize components of the physical exam performed by a qualified staff member (MD, NP, and PA) on the primary care team.

Version #: 2.8 Version Date: 11/6/2020 Page 13 of 30

9.1.5 Vital Signs

Measurement of body temperature, blood pressure, pulse and respirations will be performed and recorded each day of study participation per routine clinical care.

9.1.6 Oximetry

Oximetry will be measured on room air and on current oxygen-delivery device while the subjects are at rest during each visit unless deemed unsafe to subject to do so (e.g. patient requiring substantial amount of supplemental oxygen).

9.1.7 Other Clinical Procedures

- Imaging obtained as part of routine clinical care with be reviewed. These will include chest-imaging and CT imaging.
- Thromboelastography, if obtained part of routine care will also be reviewed and documented

9.1.8 Adverse Events

Adverse event information will be elicited during each study visit. In an effort to reduce healthcare worker exposure to SARS-CoV-2, Investigators will speak with subjects over the phone prior to entering the room to perform an abbreviated physical exam. If a subject is unable to participate in a telephonic interview, an Investigator will perform an interview to elicit adverse events in the subject's room. Appropriate documentation in case report forms will reflect subjects who are unable to participate in conversation due to altered mental status or mechanical ventilation. In addition, all clinical documentation obtained by nursing staff, as per clinical policy and standards of care, will be reviewed daily for information pertaining to adverse events. Duration (start and stop dates and times), severity/grade, outcome, treatment, and relation to study drug will be recorded on the case report form (CRF) as detailed in Section 14.

9.2 Clinical Laboratory Measurements

9.2.1 Hematology

Blood will be obtained per standard of care and sent to trial site's hematology lab for a complete blood count (hemoglobin, hematocrit, red blood cell count, white blood cell count, white blood cell differential including absolute neutrophil count, absolute bands, absolute lymphocyte count) and platelet count), serum C-reactive protein (CRP) and thromboelastography.

9.2.2 Blood Chemistry Profile

Blood will be obtained per standard of care and sent to trial site's chemistry lab for determination of serum sodium, potassium, chloride, bicarbonate, random glucose, BUN, creatinine, aspartate aminotransferase (AST/SGOT), alanine aminotransferase (ALT/SGPT), alkaline phosphatase, total bilirubin, direct bilirubin, albumin, LDH, brain natriuretic peptide (BNP), D-dimer, troponin and lactate.

Version #: 2.8 Version Date: 11/6/2020 Page 14 of 30

9.3 Research Laboratory Measurements

All samples collected during the study will be labeled with a de-identified, randomly generated specimen ID. Blood samples collected will be shipped overnight to InCell Dx at [name]. InCellDx, a diagnostics company perform PBMC purification upon receiving samples, and will bank specimens to perform analysis on blood samples, including a cytokine panel that will consist of sCD40L, GM-CSF, IFN gamma, IL-2, IL-4, IL-6, IL-8, IL-10, RANTS, TNF-alpha, and VEGF. Using PBMCs, InCellDx will also perform a CCR5 Receptor occupancy analysis. If enough plasma and PBMC samples are banked, banked samples will be sent to the The [name] Lab at the Fred Hutchinson Cancer Center near the end of the study. The [name] Lab will perform additional flow cytometric analysis to provide insight regarding the immune subset distribution and state of activation of the immune system. Additionally, up to three 100 ul alligots of banked plasma will be sent to The [name] Lab at Brown University, who will perform analysis on Chitinase 3-like 1(Chi311) at the end of the study period. Remaining specimen will be stored at InCellDx for up to six months after the end of the study, during which arrangements will be made to return remaining specimen to Lifespan/The Miriam Hospital Infection Diseases And Immunology Center. Remaining specimens will be destroyed 5 years after return to Lifespan. Until that time, these remaining specimens may be used for validation of results or may be used for further research studies.

